Diagnosis and Main Inclusion Criteria	Subjects with a biopsy proven diagnosis of differentiated thyroid cancer, and who have a scheduled appointment for definitive resection of the tumor followed by treatment with radioactive iodine at TJUH are eligible to participate.
Study Therapy, Dose, Route, Regimen	Metformin is the therapeutic agent in the protocol. The initial starting dose will be 500 mg orally daily for 3 days which then will be increased to 500 mg twice daily and, if tolerated, further increased to 1000mg twice daily after day 6. Subjects will maintain 1000 mg twice a day dosing or highest tolerated dosing until two weeks post radiation. Subjects will be randomized to 1:1 to take metformin or placebo.
Duration of administration and follow-up	The initial starting dose will be 500 mg orally daily for 3 days which then will be increased to 500 mg twice daily and, if tolerated, further increased to 1000 mg twice daily after day 6. Subjects will maintain 1000 mg twice a day dosing until two weeks post radioactive iodine treatment. The participant's medical records will be reviewed every three months, surveys administered, and CBC repeated over the course of one year according to the schedule outlined below
Reference therapy	None

Statistical Methodology	
The primary objective of the study is to estimate the impact of metformin on complete blood count and serum exosome profile following radioactive iodine treatment. All patients from whom samples are obtained both pre- and post-treatment will be included in the primary analyses. Blood counts will be compared between the RAI/Metformin group (N=16) and the placebo control RAI group (N=16). The estimated mean difference and associated 95% confidence interval will be calculated.
 
Analysis of secondary outcomes will be primarily descriptive and related to taste disturbance, xerostomia, and xerophthalmia.

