1.1 Specific Aims and Hypothesis

Primary:

- To estimate the impact of metformin on radiation-induced myelosuppression in patients treated with RAI after surgery for differentiated thyroid cancer.
- To estimate the effects of metformin on serum and salivary exosome profile in patients with well-differentiated thyroid cancer treated with total thyroidectomy and radioactive iodine.

Secondary:

- To assess safety and tolerability of metformin treatment in subjects with thyroid cancer.
- To assess the effect of metformin therapy on RAI-induced xerostomia, xerophthalmia, and dygeusia as measured by Xerostomia Questoinnaire (XC), the modified Vanderbilt Head and Neck Cancer Symposium Survey (version 2.0), University of Washington Quality of Life Questionnaire, and EORTCQLQ-H&N35

Correlatives:

- To assess the results of the radioactive iodine treatment in patients treated with metformin compared those not treated based on the outcomes of the radioactive iodine scan.

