3.0 STUDY DESIGN

3.1 General Design

Type of trial: Pilot Efficacy trial

Planned accrual period: 48 months

Planned follow-up period: 12 months

Planned enrollment: Total of 32 patients

Schema of the trial design, procedures, and stages:

Patients with a diagnosis of well-differentiated thyroid cancer who have undergone tumor resection and have indications for RAI treatment that meet our inclusion and exclusion criteria will be offered participation in this clinical trial. Patients who present to TJUH with a known diagnosis of differentiated thyroid cancer who plan to undergo surgical resection followed by radioactive iodine will be offered enrollment in the trial at the time of surgical scheduling. Patients who undergo lobectomy for atypia of undetermined significance/follicular lesion of undetermined significance or follicular neoplasm/suspicious for follicular neoplasm who are subsequently found to a malignancy will be offered enrollment at their first follow-up visit. After informed consent is signed and study subjects are randomized 1:1 to take metformin or placebo, patients will be administered metformin with dose escalation as tolerated until time of RAI treatment. There is no dose escalation for patients randomized to the placebo arm. Pre-operative and pre-RAI treatment CBC with differential will be compared to post-RAI treatment lab values. Standardized surveys assessing symptoms of xerostomia, sialadenitis, xerophthalmia and dysgeusia will be completed.

Participants' Follow-up: Participants' will have blood and saliva samples drawn post-op before metformin administration, before and immediately following RAI treatment, after metformin, and then every three months for 12 months. They will complete surveys at each post-op visit, and their medical records will be reviewed every 3 months for 12 months to assess for symptoms of myelosuppression, xerostomia, xerophthalmia, and dysgeusia. This will allow us to assess the radioprotective effects of metformin post-RAI treatment.

Purpose of the study: To estimate the radioprotective effect of metformin in subjects with differentiated thyroid cancer by evaluating both the ability of metformin to mitigate known side effects of radioactive iodine therapy as well as alter the exosome profile in the serum.

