7.0 STATISTICAL PLAN

7.1 Sample Size Determination

The sample size was chosen to have adequate precision for estimating the effect size comparing groups with respect to change from pre-resection to post-resection. From data in Bikas et al, we estimate that the standardized effect size for comparing change from pre-resection to post-resection between groups will be at least 0.78 standard deviations. For a 95% confidence interval to have half-width of 0.78 SDs, 14 patients per group are required. Allowing for 10% attrition, we will recruit and randomize 32 patients (16 per group).

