7.2 Statistical Methods

The primary objective of the study is to estimate the impact of metformin on change in complete blood count. Longitudinal measures of CBC will be modeled using mixed effects linear regression. Outcomes will be transformed as necessary (e.g., log transformed) prior to analysis. Fixed effects will include time (Pre-resection, Post-resection, 3 months post-resection, 6 months post-resection, 12 months post-resection), treatment (metformin vs. control) and treatment by time interaction. We will use a linear contrast to test the null hypothesis that change from pre-resection to post-resection is the same in the control and metformin groups. Secondary analyses will compare groups with respect to change from pre-resection to each of the follow-up times. Components of complete blood count will be analyzed with similar models.

Other longitudinally measured continuous outcomes will be modeled using mixed effects linear regression and longitudinally measured binomial and ordinal outcomes will be modeled using generalized linear mixed effects regression.

7.3 Subject Population(s) for Analysis:

All randomized participants with any data will be included in the analysis as randomized. Missing outcome data will not be imputed.

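### Sections 7.1 and 7.2 tie the primary contrast, its effect size and every model time to resection instead of RAI, and no baseline, post-RAI draw or CBC component is named as primary

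*Combined protocol and SAP*

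**What the plan says.** The primary test in 7.2 is to "test the null hypothesis that change from pre-resection to post-resection is the same in the control and metformin groups". All five levels of time in the mixed model carry the same anchor: "Fixed effects will include time (Pre-resection, Post-resection, 3 months post-resection, 6 months post-resection, 12 months post-resection". Section 7.1 does likewise for the assumed effect, "we estimate that the standardized effect size for comparing change from pre-resection to post-resection between groups will be at least 0.78 standard deviations", and then sizes the trial by precision: "For a 95% confidence interval to have half-width of 0.78 SDs, 14 patients per group are required".

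The rest of the document is built around RAI. The first aim in 1.1 is "To estimate the impact of metformin on radiation-induced myelosuppression in patients treated with RAI after surgery for differentiated thyroid cancer". The Statistical Methodology entry of the Study Summary sets out to "estimate the impact of metformin on complete blood count and serum exosome profile following radioactive iodine treatment". Section 3.1 says "Pre-operative and pre-RAI treatment CBC with differential will be compared to post-RAI treatment lab values" and lists "samples drawn post-op before metformin administration, before and immediately following RAI treatment, after metformin, and then every three months for 12 months". Appendix A (note C) and the schema time the quarterly draws from treatment, not from surgery. In the Study Summary, resection plainly means the operation that precedes RAI.

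**The concern.** Resection is not the randomised intervention. Study drug starts one week before RAI, after about 6–8 weeks of surgical recovery. The term post-resection appears only in 7.1 and 7.2 and is not defined. Taken literally, it could mean a draw made before any drug or RAI, and the 3, 6 and 12 month labels would not match the scheduled draws.

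The larger problem is what remains after the label is corrected. The primary contrast needs one baseline, one post-RAI draw and one outcome variable, and the plan fixes none of the three. Someone must choose before the headline estimate can be computed. Section 5.9 leaves the principal investigator unblinded, and 6.4.1 sends CBC results to the department, so a late choice could not be presumed blind to arm.

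**Working it through.** **1. The plan's own figure.** Inputs from 7.1: 95% interval, half-width 0.78 SD of the change, 10% attrition. A two-sided t interval for a difference of two means is assumed. Half-width = t(0.975, 2n−2) × √(2/n).

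- n = 13: 2.064 × 0.3922 = 0.810, too wide
- n = 14: 2.056 × 0.3780 = 0.777, meets 0.78
- n = 16: 2.042 × 0.3536 = 0.722

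14/0.9 = 15.6, rounded up to 16 per arm, 32 in total. The figure reproduces, and it does not depend on which draw is used because it is in SD units of the change.

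**2. Blood draws, place by place.**

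| Draw | 2.1 and 3.1 | Schema | Appendix A | Model in 7.2 |
|---|---|---|---|---|
| Pre-operative | yes | yes | not shown separately | pre-resection |
| Post-operative, before drug | yes | yes | Visit 1, timing not given | ? |
| Up to 3 days before RAI, on drug | yes | yes | no | ? |
| Up to 3 days after RAI | yes | yes | no | ? |
| End of drug, about 2 weeks after RAI (5.6) | yes | no | Visit 2 | ? |
| Months 3, 6, 12 after treatment | yes | yes | yes | labelled from resection |
| Month 9 after treatment | yes | yes | yes | absent |

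Sections 2.1 and 3.1 together give nine draws, and the model has five time levels. Four draws lie between surgery and the first quarterly visit. Only the last two of these follow RAI.

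**3. What the other sections settle.** The Study Summary and 1.1 require a value after RAI, and 2.1 compares pre- with post-treatment samples. Section 3.1 compares with post-RAI values. These exclude the two pre-RAI draws as the intended endpoint. They leave two early post-RAI draws and, from 3.1, two baselines. The draw just before RAI is taken on study drug, so a change measured from it would leave out whatever the first week of drug does. Section 2.1 lists six parameters (hemoglobin, RBC, WBC, ANC, ALC, platelets).

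**4. Follow-up labels on the literal reading (illustration).** Assume 6–8 weeks of recovery, one week of drug and no delay. RAI then falls at week 7–9 after surgery and end of drug at week 9–11. The first quarterly draw is 13 weeks later: week 20–22 if counted from RAI, 22–24 if counted from end of drug. That is 20/4.348 = 4.6 to 24/4.348 = 5.5 months after resection, against a label of 3 months (week 13). If resection is read as treatment, the labels fit.

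**5. What an open choice could cost.** If the most favourable of k contrasts were picked after the results were seen, the two-sided 5% error rate would be at most 1 − 0.95^k, the value for independent tests.

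- Two post-RAI draws: 1 − 0.95² = 9.75%
- Two baselines by two draws: 1 − 0.95⁴ = 18.5%
- Four contrasts with an assumed common correlation of 0.5, 0.7 or 0.9: 15.6%, 13.0%, 9.4%

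The correlations are assumptions; the documents give none. The open choice of component is not counted.

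**6. The effect size and timing.** Section 1.2.2 reports that the retrospective source study recorded CBC at 1, 6 and 12 months. The two early post-RAI draws fall no more than 3 days and about 2 weeks after RAI. Section 1.2 puts leukocyte and platelet nadirs 1–2 months after RAI, later than both. The documents do not say which source time or component gave 0.78 SD.

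**The case against.** The best defence is that this is a slip of terminology. The aims, the synopsis and 3.1 all point to RAI, and reading resection as treatment makes the 3, 6 and 12 month labels fit. Appendix A has a single end-of-treatment draw before follow-up, which resembles the model's layout and favours the end-of-drug draw. Section 2.1 mentions recovery of white cell count, which hints at a component. The trial is a 32-patient pilot aimed at estimation, and 7.2 already compares the arms at each follow-up time.

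Much of this stands. A reader might infer that the primary test compares the arms before any drug or RAI and so has a true difference of zero, or that all four post-surgical draws fit the plan equally well. The documents do not support either reading, because several sections place the endpoint after RAI. A reader might also make much of 4.1, which sets no limit on time since earlier surgery. Since 3.1 and 6.1 describe enrolment close to biopsy, surgery or the first follow-up visit, and the literal labels are probably unintended, that is no measure of the problem. Nor can 0.78 SD be shown to be wrong: 7.1 says at least that much, and the source data are not in the documents.

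The defence does not supply the missing choices. Sections 2.1 and 3.1 schedule both early post-RAI draws, and the schema omits the very draw that Appendix A favours. Section 3.1 names two baselines. The remark on white cells names no primary component, and 7.2 treats components as further analyses. The pilot status lowers the stakes, but the headline estimate stays undetermined.

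**Conclusion.** The concern holds. As written, the primary contrast and the model times have the wrong anchor. With the anchor corrected, two baselines, two early post-RAI draws and six parameters remain, with none named primary. The error-rate ceilings of 9.75% and 18.5% describe the freedom left if the choice were made after seeing results; nothing in the documents says that it will be. The 20–24 week offset applies only to the literal reading and the no-delay assumption.

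The sample size is not in question. The basis of 0.78 SD as an expected effect is unstated, which is a reporting gap and not a demonstrated error. The contrast should be settled before outcome data by arm are seen, because the primary analysis cannot be run without it.

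**What to change.** - In 7.1 and 7.2, replace the resection labels with the named scheduled draws. State whether follow-up time counts from RAI or from end of study drug, and include the 9-month draw.
- Define the primary contrast as the between-arm difference in change from one named pre-drug baseline to one named post-RAI draw, for one named CBC component. The pre-operative draw and the post-operative draw before study drug both qualify as baseline, since neither can be affected by the drug. Record the choice before outcome data by arm are seen.
- In choosing the draw, address the 1–2 month nadir in 1.2, which is later than both early draws, and say why the chosen time serves the aim.
- Reconcile the lists of draws in the Study Summary, schema, 2.1, 3.1 and Appendix A with that contrast.
- Keep 14 evaluable and 16 randomised per arm as a precision statement. State which time and CBC component of the source study gave 0.78 SD, or drop it as an expected effect.

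The cost is wording in these sections, three recorded decisions (baseline, draw, component) and one check of the source study. All samples are already planned, and the number of patients does not change.

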8.0 SAFETY AND ADVERSE EVENTS

8.1 Definitions

Adverse Event

An **adverse event** (AE) is any symptom, sign, illness or experience that develops or worsens in severity during the course of the study. Intercurrent illnesses or injuries should be regarded as adverse events. Abnormal results of diagnostic procedures are considered to be adverse events if the abnormality:

- results in study withdrawal
- is associated with a serious adverse event
- is associated with clinical signs or symptoms
- leads to additional treatment or to further diagnostic tests
- is considered by the investigator to be of clinical significance

Serious Adverse Event

Adverse events are classified as serious or non-serious.

A **serious adverse event** is any AE that is:

- fatal
- life-threatening
- requires or prolongs hospital stay
- results in persistent or significant disability or incapacity
- a congenital anomaly or birth defect
- an important medical event

Important medical events are those that may not be immediately life threatening, but are clearly of major clinical significance. They may jeopardize the subject, and may require intervention to prevent one of the other serious outcomes noted above. For example, drug overdose or abuse, a seizure that did not result in in-patient hospitalization, or intensive treatment of bronchospasm in an emergency department would typically be considered serious.

All adverse events that do not meet any of the criteria for serious should be regarded as **non-serious adverse events**.

Adverse Event Reporting Period

The study period during which adverse events must be reported is normally defined as the period from the initiation of any study procedures to the end of the study treatment follow-up. For this study, the study treatment follow-up is defined as 15 days following the last administration of study treatment.

Preexisting Condition

A preexisting condition is one that is present at the start of the study. A preexisting condition should be recorded as an adverse event if the frequency, intensity, or the character of the condition worsens during the study period.

General Physical Examination Findings

At screening, any clinically significant abnormality should be recorded as a preexisting condition. At the end of the study, any new clinically significant findings/abnormalities that meet the definition of an adverse event will be recorded and documented as an adverse event.

Post-study Adverse Event

All unresolved adverse events will be followed by the investigator until the events are resolved, the subject is lost to follow-up, or the adverse event is otherwise explained. At the last scheduled visit, the investigator will instruct each subject to report any subsequent event(s) that the subject, or the subject's personal physician, believes might reasonably be related to participation in this study. The investigator will notify the sponsor of any death or adverse event occurring at any time after a subject has discontinued or terminated study participation that may reasonably be related to this study. The sponsor will also be notified if the investigator should become aware of the development of cancer or of a congenital anomaly in a subsequently conceived offspring of a subject that has participated in this study.

Abnormal Laboratory Values

A clinical laboratory abnormality should be documented as an adverse event if any one of the following conditions is met:

- The laboratory abnormality is not otherwise refuted by a repeat test to confirm the abnormality
- The abnormality suggests a disease and/or organ toxicity
- The abnormality is of a degree that requires active management; e.g. change of dose, discontinuation of the drug, more frequent follow-up assessments, further diagnostic investigation, etc.

Hospitalization, Prolonged Hospitalization or Surgery

Any adverse event that results in hospitalization or prolonged hospitalization should be documented and reported as a serious adverse event unless specifically instructed otherwise in this protocol. Any condition responsible for surgery should be documented as an adverse event if the condition meets the criteria for an adverse event.

Neither the condition, hospitalization, prolonged hospitalization, nor surgery are reported as an adverse event in the following circumstances:

- Hospitalization or prolonged hospitalization for diagnostic or elective surgical procedures for a preexisting condition. Surgery should **not** be reported as an outcome of an adverse event if the purpose of the surgery was elective or diagnostic and the outcome was uneventful.
- Hospitalization or prolonged hospitalization required to allow efficacy measurement for the study.
- Hospitalization or prolonged hospitalization for therapy of the target disease of the study, unless it is a worsening or increase in frequency of hospital admissions as judged by the clinical investigator.

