Treatment with I-131 can also result in disturbed nasolacrimal gland function and xerophthalmia resulting from inflammation of lacrimal gland. Recent studies have shown evidence of xerophthalmia in 16-33% of patients lasting for up to 2 years. (Van Nostrand 2009) A recent review reported that an abnormal Shirmer's test was found significantly more frequently in patients exposed to I-131 compared to unexposed patients. (Clement 2015) RAI uptake by nasolacrimal duct mucosa leads to subsequent inflammation, edema, and fibrosis and can be responsible for lacrimal duct obstruction and resulting chronic epiphora. (Fard-Esfahani 2014). Conjunctivitis has also been reported in 23% of patients. (Van Nostrand 2009)

Leukopenia, thrombocytopenia, and anemia are major risks of I-131 therapy. (Van Nostrand 2009) Of the known potential adverse events of I-131 therapies, bone marrow suppression has been considered the most important. (Bikas 2016) More than 20 publications have described bone marrow suppression secondary to I-131 therapy, though most are underpowered. Bone marrow suppression is mostly transient and results in a decreased in white blood cell and platelet count for up to 6-10 weeks. Total incidence is about 25% with leukocyte and platelet count nadirs 1-2 months after RAI administration (Fard-Esfahani 2014) Occasionally it results in increased susceptibility to infection or bleeding if the marrow dose exceeds about 200 cGy. (Fard-Esfahani 2014)

Of those patients receiving high-activity therapies, 38% have grade 1 bone marrow suppression as defined by the World Health Organization (WHO). Previous research has shown that even a single dose of RAI can cause changes in the peripheral CBC. (Padovani 2014) The degree to which an individual is affected is influenced by many factors including the patient's clearance rate, the total cumulative prescribed activity of I-131, the frequency of therapy and interval between treatments, the patient's bone marrow reserve and the degree to which bone metastases are present. Interpretation of the hematologic effects of RAI therapy is complicated by the fact that many patients who require high cumulative activities of RAI also receive external beam radiation therapy (EBRT) to treat metastatic lesions to the bone, which carries its own hematopoietic toxicity (Padovani 2014)

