There are currently multiple ongoing studies using doses from 500 mg twice daily up to 2500 mg per day in the treatment arms. There are also studies using the extended release form for a dose of 1500 mg daily. We have chosen our starting dose and escalation regimen to minimize side effects. The chosen standing dose is based on metformin's therapeutic range (minimal therapeutic dose in diabetic patients is 1500-2000 mg a day)^{28, 29}. The time of planned exposure to metformin will be 3 weeks. We will allow a window of an additional 2 weeks in the event that there are delays in the treatment scheduling but no patients will receive metformin for more than 35 days.

Rules for dose modification: Toxicity monitoring, dose modification and treatment of complications:

Particular attention will be paid in the first three days of treatment. Patients will take 500 mg/day for 3 days. From day 4, 500 mg twice daily and then in 3 days dose escalation to 1000 mg twice daily will be achieved. A phone call on the day of each dose escalation will be made in order to evaluate the tolerability of the drug and also weekly thereafter. Patients will be instructed to contact the clinical investigators should any side effects occur during the study¹⁹.

In the event that an iodinated IV contrast dye load for CT scanning is required at some point during the metformin treatment period, the drug will be stopped the day before IV dye administration, as is the standard practice among patients taking metformin. However, IV contrast dye generally precludes treatment with RAI as the iodinated contrast competes with RAI and thus limits its effect. Therefore, it is extremely unlikely that any patient will be receiving iodinated contrast at the time of the study. Furthermore, this measure is generally considered to be conservative as the risk of lactic acidosis in patients taking metformin has not been shown to be higher than that of the general population after IV contrast dye in recent literature. Nevertheless, this measure is in compliance with current American College of Radiology guidelines^{30, 31}. Metformin will be resumed the day after RAI treatment completion at the last dose the subject was receiving prior to being held and if escalation was planned as previously described.

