5.10.3 Dispensing of Study Drug The study drug will be dispensed to the participants in 1 bottle containing approximately 69 500mg tablets for a maximum of 3 weeks. The bottle will be labeled "The bottle will be labeled "take one tablet daily for three days then one tablet twice daily for three days then two tablets twice daily until the day before the RAI treatment. Resume two tablets twice daily the day after RAI treatment completion until the end of the bottle." The amount of pills dispensed to every participant will be logged in the accountability logs by the pharmacist. The participant will be instructed to bring the bottle and all the pills that were not taken the day of his surgery. Regular study drug reconciliation will be performed only at the end of the study.

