5.11 Placebo

Placebo will be given as 500mg capsules twice daily. Placebo will be in capsule form. It will be stored in a locked cabinet until given to the participants at room temperature in the Thomas Jefferson University Hospital Investigational Drug Service (IDS) Pharmacy.

The placebo will be packaged in bottles containing approximately forty-two (42) 500mg capsules. The bottle will be labeled "take one capsule twice daily until the day before the RAI treatment. The day after RIA treatment completion, resume one capsule twice daily until the end of bottle.".

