6.0 STUDY PROCEDURES

6.1 Study Visit Schedule Screening: Trial Coordinator will screen the office charts for possible inclusion in the trial. Labs for the screening part will be available from pre-admission testing that is standard of care for initial biopsy. Women of childbearing potential (WOCBP) should have a pregnancy test done as part of pre-admission testing prior to surgery (within 14 days of study enrollment). If a test was not done, it will be done at time of consent.

Visit 1: Subjects who meet inclusion criteria after reviewing the initial biopsy, laboratory data, and clinical chart will be approached the day of their follow up after initial biopsy. The study coordinator will meet with the prospective candidates and go over the protocol, answer questions and obtain informed consent. If the subject is agreeable to the study, a physical exam will be performed, subject will be randomized and metformin or placebo will be dispensed. Instructions on how to take study drug will be given and times for follow up phone calls for tolerability and safety will be arranged with participants. Participants will be instructed to call with any side effects or adverse events that occur in the interim of the follow up phone calls.

The exact date to start the metformin will be determined this visit based on the planned date of radioactive iodine (RAI) administration. One week prior to the radioactive iodine treatment, the first dose of metformin can start. Metformin or placebo will be stopped the day before RAI treatment is received.

Per standard of care, a pregnancy test will be done within 72 hours of starting radioactive iodine administration.

Quality of life measures will be assessed prior to start of metformin.

Quality of life measures will be administered on an IPad through a website (https://az1.qualtrics.com/jfe1/preview/SV_57qgtgkjaexOy9f). Participants will be

identified only by study ID number. Paper questionnaires will be provided if the forms cannot be completed electronically.

Metformin or placebo administration will resume the day after the last treatment with radioactive iodine and will be taken until the end of bottle (2 weeks after RAI treatment).

Visit 2: At the first visit following completion of metformin administration for two weeks after RAI, patients will be approached for bottle and pill reconciliation, review of compliance with appropriate lab draws, as well as follow up of side effects and adverse events.

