Follow-up: A follow up phone call will be performed 2 weeks after the last dose of metformin for any other side effects or adverse events. Every 3 months during the first year post-treatment subjects will have their regularly scheduled appointments at which we will draw blood/saliva, administer quality of life surveys, and review medical records.

Quality of life measures will be administered on an IPad through a website (https://az1.qualtrics.com/jfe1/preview/SV_57qgtgkjaexOy9f). Participants will be identified only by study ID number. Paper questionnaires will be provided if the forms cannot be completed electronically.

6.2 Definition of Dose-Limiting Toxicities and early stopping rules:

Toxicity will be evaluated using the most recent version (version 4) of the NCI toxicity criteria, i.e. the NCI Common Terminology Criteria for Adverse Events (CTCAE) version 4.0. The CTCAE provides descriptive terminology and a grading scale for each adverse event listed. A copy of the CTCAE can be found at <http://ctep.cancer.gov>.

Grade 4 toxicity (probably or definitely drug related): Treatment will be permanently discontinued.

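### Mandatory AE reporting ends about day 29 after RAI, before most or all of the 1-2 month marrow nadir, so non-serious events that start then need not be reported

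*Combined protocol and SAP*

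**What the plan says.** - **Reporting period (8.1, Adverse Event Reporting Period).** AEs must be reported from the first study procedure to the end of study treatment follow-up. "For this study, the study treatment follow-up is defined as 15 days following the last administration of study treatment".
- **Dosing (6.1).** "One week prior to the radioactive iodine treatment, the first dose of metformin can start". Drug stops the day before RAI, resumes the day after, and runs until the bottle is empty, which 6.1 gives as two weeks. Section 5.10.3 dispenses "1 bottle containing approximately 69 500mg tablets for a maximum of 3 weeks"; section 5.11 gives placebo patients "approximately forty-two (42) 500mg capsules". For scheduling delays, section 1.4 allows two extra weeks but says that "no patients will receive metformin for more than 35 days".
- **AE contact in follow-up (6.1).** "A follow up phone call will be performed 2 weeks after the last dose of metformin for any other side effects or adverse events". Appendix A, note I, makes this call the follow-up AE assessment. For the 3-monthly visits the schedule lists blood, saliva, questionnaires and record review, with no further AE assessment.
- **Expected timing of marrow toxicity (1.2).** "Total incidence is about 25% with leukocyte and platelet count nadirs 1-2 months after RAI administration". The same section has counts depressed for up to 6-10 weeks, with occasional susceptibility to infection or bleeding at higher marrow doses.
- **Provisions reaching past the window.** Section 8.2 has the investigator ask about AEs whenever the subject is contacted, but records those in the study period. It also requires later serious AEs (SAEs) judged possibly related to treatment or participation to be reported immediately. Sections 8.1 and 8.2 follow events already open. Section 3.1 has records reviewed every 3 months for symptoms of myelosuppression.

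**The concern.** Myelosuppression after RAI is what metformin is meant to reduce, and safety is a secondary objective. Yet the AE period is counted from the last dose of study drug, not from RAI, which is the source of the marrow toxicity. If it closes before the time when the protocol itself expects counts to be lowest, a non-serious infection, a minor bleed or a symptomatic cytopenia that starts then falls outside mandatory reporting. The monitoring committee reviews reported AEs and SAEs (8.5, 8.5.2), so it need not see such events either.

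Counting from the last dose has a second consequence. A patient who stops drug early also leaves AE reporting early. If stops for tolerability differ between metformin and placebo, the time under AE observation differs by arm.

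**Working it through.** Take RAI as day 0, given once; drug started 7 days earlier; full adherence; one month as 30.4 days.

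**1. Does the dispensed supply reproduce the two weeks after RAI?**
- Metformin before RAI: 3 days × 1 + 3 days × 2 + 1 day × 4 = 13 tablets. After RAI: (69 − 13) / 4 = 56 / 4 = 14 days.
- Placebo before RAI: 7 × 2 = 14 capsules. After RAI: (42 − 14) / 2 = 28 / 2 = 14 days.

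Both bottles agree with 6.1: the last dose is on day 14.

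**2. When does AE reporting close on the planned schedule?** 14 + 15 = day 29. The phone call falls on 14 + 14 = day 28.

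**3. What period does section 1.2 point to?** Nadir: 1 × 30.4 to 2 × 30.4, about days 30 to 61. Depressed counts: up to 6 × 7 = 42 to 10 × 7 = 70 days.

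**4. How far does the closing day move?**

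| Scenario | Last dose | Reporting closes | Short of day 61 by | Short of day 70 by |
|---|---|---|---|---|
| Planned schedule | day 14 | day 29 | 32 days | 41 days |
| Stopped for good the day before RAI | day −1 | −1 + 15 = day 14 | 47 days | 56 days |
| Metformin halved after RAI, bottle finished | 56 / 2 = day 28 | 28 + 15 = day 43 | 18 days | 27 days |
| Exposure stretched to 35 days, all extra time after RAI | 35 − 7 = day 28 | 28 + 15 = day 43 | 18 days | 27 days |

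On the planned schedule the whole nadir range lies after closure, though at its early edge by only 1-2 days. In the two longest scenarios the window covers about 43 − 30 = 13 of the 61 − 30 = 31 days. To reach day 70 after a last dose on day 14, the period would have to run 70 − 14 = 56 days after that dose, not 15.

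**5. Would blood counts fill the gap?** Section 2.1 schedules complete blood counts (CBCs) within three days after RAI, at the end of metformin (about day 14) and then every three months. With the first of those at about day 91, nothing is drawn for 91 − 14 = 77 days, which contain the whole nadir range.

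**6. How precise would a comparison by arm be?** At the cited 25% incidence with 16 per arm, the 95% half-width for a risk difference is 1.96 × √(2 × 0.25 × 0.75 / 16) = 0.30, or about ±30 percentage points. Such a table can only be descriptive.

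**The case against.** The strongest defence is that the safety objective concerns metformin, so a window tied to dosing is a reasonable choice, while marrow effect is measured by CBC. The protocol also has several nets beyond day 29. An admission for infection or bleeding is an SAE and is reportable at any time if judged possibly related. Events that began earlier are followed. Section 8.2's questioning has no time limit, 8.1 defines an AE by the course of the study and records new findings at its end, and records are searched for myelosuppression for a year.

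Much of this stands. A reader might infer that events at the nadir go unreported altogether; the documents do not support that. What the nets leave open is the non-serious event that starts after closure:
- The late-SAE clause needs seriousness and a judgement of relatedness, and section 5.9 leaves the principal investigator and assessing care providers unblinded.
- The duty in 8.1 to notify the sponsor of related late events applies after a subject has ended participation, so it does not clearly cover patients still in follow-up.
- No text sends the findings of the record review to AE forms or CTCAE grading.
- Asking at every contact conflicts with the reporting period in 8.1 and with Appendix A, note I. The text does not settle which governs.

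Two other inferences also fail. One is that the window prevents comparison of AEs by arm: section 7.2 names no such AE analysis for any period, and it does compare blood counts by arm. The other is that 0.25 × 32 = 8 patients would have missed AEs. That figure is expected suppression. It ignores any benefit of metformin, and it includes suppression that begins before closure and is followed. The number of missed AEs cannot be derived from the documents.

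It is also fair to say that a longer AE period alone would not find asymptomatic cytopenia.

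**Conclusion.** The point holds in a limited form. The mandatory period and the last scheduled AE contact end about days 28-29 after RAI on the planned schedule, ahead of the cited nadir range. Across the scenarios examined, closure ranges from about day 14 to about day 43, and none reaches day 61. The loss is confined to non-serious haematologic, infection and bleeding events that start after closure, and its size in events is unknown. The contradiction between 8.1, 8.2 and Appendix A stands whatever the timing.

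This rests on the nadir timing quoted in section 1.2, a single RAI administration and the dispensing figures. It should be corrected, because the uncovered period is the one in which a trial of marrow protection most expects harm and a suitable visit already exists. The missing CBC between about day 14 and month 3 is a separate gap.

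**What to change.** 1. In 8.1, define the end of the AE period by time since RAI, the same for both arms and independent of when drug stopped. Extend it through the existing 3-month post-RAI visit, at least for haematologic, infection and bleeding events graded by CTCAE 4.0.
2. In Appendix A, add an AE assessment at that visit and amend note I.
3. Reconcile 8.1, 8.2 and Appendix A, so that it is clear whether non-serious events learned of at later contacts or in record review are recorded as AEs.
4. In 7.2, add a descriptive table of these events by arm, without a formal test.

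The cost is some AE questions at a visit already planned and a few more AE forms. The limitation is recall: at about day 91 patients would be asked about events mostly one to two months old. Asymptomatic cytopenia at the nadir would still be missed, and closing that gap is a matter for the CBC schedule.
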